Research team members may also be involved in safety monitoring throughout the study. Although not expected, research staff will be prepared to address any negative reactions to study procedures including audio recording of the conversation with the surgeon, survey questions and open-ended interviews. All negative reactions will be reviewed to determine whether a change in protocol is necessary. The PI ([name]) will report any policy violations to the IRB immediately. The PI will also report any adverse events in compliance with the IRB policy for reporting. In addition to the DMC, the PI will review the research study and the accrued data on a monthly basis in project meetings so as to ensure the validity and integrity of the data and to evaluate whether changes to the anticipated benefit-to-risk ratio of study participation have occurred.

Data coding

All coding will be completed prior to unblinding.

Coding of number and types of questions will follow a pre-defined coding scheme (Table 2). We developed a detailed codebook based on an established coding scheme³¹ as noted in the PCORI proposal. Coders coded each question by speaker and question type/content area. The coding schema was tested twice, with acceptable intraclass correlation found between coders. The first round of testing drew a random sample of 45 transcripts from a prior project. Intraclass correlations were acceptable for all but one question category. We reviewed all discrepancies for this category and revised the codebook. The second round of assessment was comprised of a random set of 30 transcripts from this project. Coders were blinded to arm status of the transcripts. This sample was generated by the independent statistician who maintains our blinding procedures and synthetic study ID's. We found an acceptable ICC for all question categories, as shown in Table 3.

Table 2: Predefined coding scheme to characterize questions asked by patients and family members during surgical consultation (T₀)		
Category	Definition	Example
Options	Seeks to understand different treatment pathways.	"Is there another way?"
Expectations	Seeks to understand what life would look like after treatment.	"Like, you know, how long will be the recovery?"
Advance Directives	Asks about care and consequences if patient is unable to speak for him/herself.	"Then, you know, why continue?"

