The goal of evaluating MYCaW is to test how much participant-reported concerns change over time for patients who did and did not receive the QPL. Our understanding of the MYCaW measure evolved since the start of the study based on the blinded coding of MYCaW data which revealed a much wider range of problems and concerns in response to MYCaW items than our previous and current review of the literature would suggest. Because not all patients in our study will plan to have surgery after meeting with a surgeon, there is heterogeneity in the description of concerns that is dependent on their treatment plan. Without changing our pre-specified analytic plan, we believe we will have findings that are extremely difficult to interpret. Furthermore, if an effect (positive or negative) of the intervention is identified, it would be challenging to assist surgeons and patients in using these results as many different types of concerns will be lumped together. These proposed changes are responsive to the data and the setting of this trial.

As such, we will conduct a stratified analysis based on the post-randomization variable of a treatment plan to have surgical intervention as determined by the T0 conversation with the surgeon. To this end, our analysis will exclude patients whose treatment plan did not include surgery upon leaving the surgical consultation at T0, and whose treatment plan was unclear at the end of the T0 consultation (this corresponds to categories #2 and #3 below regarding the “treatment plan”).

Within the cohort of patients whose treatment plan includes surgery, we will compare intervention to control patients who noted similar concerns. We will first categorize participants (both patients and family members) by the primary (first) concern expressed and then compare the respondent-reported rating of that concern, assessing the mean score between treatment groups for each category. We will next separate respondents by type: patient and family and repeat this analysis. We will also compare the change of the respondent’s (patient or family member in separate groups) rating of that concern between T1 and T2 using a respondent-level random effects model. We will similarly analyze the change between T1 and T3.

Secondary outcomes: Aim-1: patient engagement [PEPPI-5, OPTION5, HCCQ]

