This code includes a broad range of questions about technical or logistical aspects of surgery/treatment but also the health condition itself: Why do I have this? What's going on here?

- Includes any questions that reference surgical instruments, length of surgery, medications, surgeon expertise, surgeon practice patterns, surgical technique or procedure (see Appendix A for examples of techniques) surgery names and technique names, locations on surgery day, pre-op instructions, timing issues
- Includes specific questions about anatomy and physiology*, surgery, medications, blood products, surgeon expertise, institutional quality/expertise** practice patterns (who actually does the surgery, how many times per year this surgeon does it, etc.)
 - * These changes may include things such as cell or organ level functions/changes. Questions about physiological or anatomical changes *up to and during* the treatment are coded as logistics. Questions about these changes occurring *following* treatment are coded as expectations.
 - **Sometimes people ask about other institutions (like Mayo Clinic) but their question is not really about going there or the logistics of having treatment at another institution. What they're really asking about it is whether the procedure they do there could be done here. In this case, the question should be coded as "OPTIONS". Read questions asking about other institutions carefully as they could fall under logistics or options.
- Includes questions on location of providers and services only if they relate to the health condition and treatment being discussed
 - Example: "Is it here in this building?" would be coded as "LOGISTICS" if it's a question of where the patient's loved ones would wait for them during surgery.
 - If it was a question about where another doctor practices who is not involved in their care for the health condition being discussed with the surgeon, this would be coded as "OTHER".

- For example, if a patient and surgeon are discussing the town the patient lives in and the patient says, “Oh do you know, Dr. X? He’s my neighbor! Do you know where he works?” without any reference to Dr. X being involved in their care, this would be coded as “OTHER”.

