- Includes questions about other doctors or medical personnel but only when they are related to the health condition prompting the surgical consult (questions such as “Should I let my PCP know I’m scheduled for surgery?” should be coded as “LOGISTICS” but questions about other doctors unrelated to the condition being discussed are coded as “OTHER”- an example of this would be “Do you know Dr. X?” where there is no connection between Dr. X and their condition described)
- “LOGISTICS AND TECHNICAL CONCERNs” examples:
 - “How long does the surgery take?” or “Any idea of timing?” [When will surgery be?]
 - “How will blood drain from...after you take the vein out?”
 - “Is this something like, this is not uncommon for you people?”
 - “So how many bypasses are there?”
 - “Yeah, how long do you think this has...?” [referring to discussion of blockages building up]
 - “Do you work with him a lot?” [Though note that this is coded as “LOGISTICS” only if it’s asking about a doctor involved in the treatment of their condition being discussed with the surgeon. If this was about a doctor unrelated to the health condition being discussed, this would be coded as “OTHER”]
 - “But that other way is easier to get to? [This is coded as “LOGISTICS” as opposed to is there another option]”
 - “Which valve?”
 - “What does TAVI stand for?”

EXPECTATIONS

Questions about what will happen AFTER surgery, including in the immediate, post-operative period right after surgery. Use the time period in the question as your guide on when to use this code- it must relate to something after surgery. “If we do this, what’s gonna happen after surgery?” is the main point of this topic area.

This topic area includes questions that seek to understand how the patient’s life will change or remain the same following a specific treatment option, particularly in terms of quality of life and patient reported outcomes. Look for words like: feeling, after-effect.

- Includes patient reported outcomes such as quality of life, recurrence, changes in energy levels, mobility, continence, scarring, wound-care, bags/drains/tubes after surgery, rehab details, recovery time, limitations in function or other capacity, durability of procedure (for example how long will my new heart valve last?), length of hospital stay after surgery,

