- Note: questions about the length of the surgery or procedure are coded under logistic/technical concerns, NOT expectations because this question relates to the procedure itself, not what happens after
- Note: questions about physiological or anatomical changes *following a treatment* are coded under EXPECTATIONS. These changes may include things such as cell or organ level functions/changes

- “EXPECTATIONS” examples:
 - “Like, you know, how long will be the recovery?”
 - “Like my nose going to be running all the time or?”
 - “Right, but would there be any additional pain?”
 - “It like, I mean, do you have a timeline historically when it would start to . . . regenerate again or grow again?”
 - “These are maybe questions for later, but since they're on my mind now, when can he take aspirin again?”
 - “After the two weeks [post-op] or even during those two weeks, can he go visit him or not?”
 - “So how long would he need somebody with him kind of 24 hours after he gets home?”

RISKS/COMPLICATIONS

This topic area includes questions that seek to understand what could go wrong during or following the treatments options that are being discussed (operating, not operating, chemo, radiation, etc.)

Technical discussion of near-term, surgeon-defined complications (e.g. 30 days). Look for words like: risks, complications, chances, odds. Note that this includes the risks of not operating as well as risks associated with surgery or other treatment options.

- Include any questions that reference short-term, surgeon defined effects from treatment including extended hospital stay, extended recovery time, blood clotting, bleeding, etc.
- “RISKS” VS “EXPECTATIONS” code: Code any questions that reference long-term effects/outcomes including recurrence, durability of procedure as “EXPECTATIONS”, not “RISKS”
 - Be careful about the context: is the patient specifically asking about *how it's going to get done* or about *bad outcomes*? (*How it's going to get done* would go under “LOGISTICS AND TECHNICAL CONCERNS”—even if it's serious or dangerous. Whereas questions on *bad outcomes* are coded as “RISKS”)
 - If the question is *comparing* risks of two or more treatment options, code this as “OPTIONS”
- “RISKS/COMPLICATIONS” examples:
 - “How many people have to be on a ventilator after?”
 - “As far as the location of the tumor that remains in those veins and stuff, is everything, is anything at risk as far as, I don't know, blood flow function of any of those parts?”

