These discussions generated the first decision support target for our QPL: "Should I have surgery?" Our PFAC wanted patients to deliberate about having surgery and receive explicit information about how surgery might improve symptoms or longevity. To address this need, our stakeholders selected the question prompts:

- "What are my options?"
- "What is likely to happen if I do have surgery? If I don't have surgery?"
- "Will surgery make me feel better?" and
- "Will surgery help me live longer? If so, how much longer?"

Expectations

The PFAC explored qualitative data suggesting patients were unprepared for what occurred postoperatively. For example, 1 patient noted she had been apprised of specific risks, but did not recognize this information could be used to prepare for complications or prolonged recuperation. She described how frightened she was by her slow recovery and postoperative weakness:

No, no I wasn't expecting anything. They didn't tell me there could be [complications]. They did say you could develop A-fib and they did say that after the operation you could have a stroke or heart attack....So I didn't really, I did ask questions, but I guess I didn't ask if it would be a long recovery or what could happen...I mean you're not expecting, and I don't think you know all the questions you should ask.

Although surgeons named risks and described operations under consideration as *big surgery*, patients struggled to translate this information. Patients assumed they would return to normal postoperatively: “If I can’t come back normal, I don’t want to come back.”

The PFAC expressed concern that patients underestimated the impact of surgery and had a naive outlook about the seriousness of surgery, leading to surprise or distress when recovery was arduous. This notion was familiar to PFAC members who reported feeling “blindsided” postoperatively. They worried that what was normal after surgery for the surgeon was not normal for the patient and this might cause distress when the surgeon’s expected outcome was unexpected by the patient.

This discussion generated the target: “What should I expect if everything goes well?” The PFAC chose question prompts to prepare for recovery and long-term physical changes, including:

- “How do you think my daily life will look after surgery? Right after surgery, 3 months later, 1 year later?”
- “Will I have any tubes or drains put in during or after surgery? Will I need them at home?”

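### The codebook's rule that an EXPECTATIONS question must concern something after surgery conflicts with Table 2 and with the codebook's own wider wording, so some questions about non-surgical treatment have no settled code on this primary endpoint

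*Combined protocol and SAP*

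**What the plan says.** The plan makes the number of EXPECTATIONS questions (0, 1, 2+) a primary outcome of Aim 1. Under the modified plan it is tested at 0.0125 (Updated analysis plan and modified power analysis).

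Two kinds of wording set its scope.

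- **Wide.** Table 2 (Data coding) gives the definition as "Seeks to understand what life would look like after treatment". The second paragraph of the manual's EXPECTATIONS section covers how the patient's "life will change or remain the same following a specific treatment option". A note in that section says physiological or anatomical changes after a treatment "are coded under EXPECTATIONS. These changes may include things such as cell or organ level functions/changes". The LOGISTICS section agrees: such changes following "treatment are coded as expectations".
- **Narrow.** The first paragraph of the EXPECTATIONS section is about what happens after surgery and adds that "it must relate to something after surgery". The LOGISTICS section, and the LOGISTICS versus EXPECTATIONS entry in the manual's Appendix A, put the boundary at the post-operative stage.

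Each question receives one topic code, and each transcript has one coder for question type. LOGISTICS and OTHER are not primary outcomes.

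**The concern.** The enrolled patients do not all end with an operation. The plan notes that "not all patients in our study will plan to have surgery after meeting with a surgeon", and the manual itself lists chemotherapy, radiation and observation among the treatments discussed. Questions about life after those treatments are foreseeable. If the narrow sentence is applied literally, such a question can leave the primary endpoint for LOGISTICS or OTHER. On a 0, 1, 2+ scale the loss of one question can move a patient down a category.

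The loss could also differ by arm. Only intervention patients are sent the QPL, and three of its four expectation prompts name surgery, for example "How do you think my daily life will look after surgery". Under the narrow rule, a change in which treatment patients name could change the score without any change in how often they ask what to expect.

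**Working it through.** **1. The texts side by side.** Take the question *how will I feel after the radiation?*, asked about that treatment alone.

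| Place | Rule in substance | Result |
|---|---|---|
| Table 2 | life after treatment | EXPECTATIONS |
| EXPECTATIONS, first paragraph | must concern a time after surgery | not EXPECTATIONS |
| EXPECTATIONS, second paragraph | life after a specific treatment option | EXPECTATIONS |
| OPTIONS versus EXPECTATIONS or RISKS | life within one given treatment, no comparison | RISKS or EXPECTATIONS |
| Appendix A, OPTIONS entry | life with a certain option, no comparison | RISKS or EXPECTATIONS |
| Appendix A, LOGISTICS versus EXPECTATIONS | post-operative stage onward | not clearly EXPECTATIONS |
| RISKS | what could go wrong, including with chemotherapy, radiation or no operation | only if it asks about harm |
| OPTIONS | comparison of two or more options | no, one treatment only |

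The notes on changes after treatment concern anatomy and physiology, so they do not settle this example. If the narrow sentence prevails, LOGISTICS or OTHER remains. No text gives an order of precedence.

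**2. Scale, for illustration.** The plan states no figure on this point, so there is none to reproduce. Inputs:

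- The plan's worst case puts 65% of controls in the zero category. I assume this holds under the wide definition and in both arms, so the share who ask is 1 − 0.65 = 0.35 and there is no true effect.
- A share s of askers asks only about non-surgical outcomes and is scored zero: s_C in control, s_T in intervention. The documents give neither, so the values below are assumptions.

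With a = 0.35(1 − s_C) and b = 0.35(1 − s_T), the apparent odds ratio for any question against none is [b/(1 − b)] / [a/(1 − a)].

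Example, s_C = 0.20 and s_T = 0.10: a = 0.280, b = 0.315, and (0.315/0.685)/(0.280/0.720) = 0.4599/0.3889 = 1.18.

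| s_C | s_T = 0 | s_T = s_C/2 | s_T = s_C |
|---|---|---|---|
| 5% | 1.08 | 1.04 | 1.00 |
| 10% | 1.17 | 1.08 | 1.00 |
| 20% | 1.39 | 1.18 | 1.00 |
| 30% | 1.66 | 1.31 | 1.00 |

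The reverse is equally open. With s_C = 0.10 and s_T = 0.20 the ratio is 0.3889/0.4599 = 0.85. The calculation reduces the three-level endpoint to two levels and ignores the surgeon effect.

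**The case against.** The strongest reply is that the narrow sentence is only a time boundary. It follows an instruction to go by the time the question refers to, LOGISTICS uses the same device for the period up to and through surgery, and Appendix A repeats the boundary under that pairing. On this reading no non-surgical treatment is barred. The manual also tells coders to use the surrounding conversation, most of its EXPECTATIONS examples never name surgery, and it warns against using OTHER as a fallback. Some non-surgical questions still score on a primary endpoint, as RISKS or OPTIONS. Eligibility requires a problem that surgery could treat, and a planned restricted analysis drops dyads where major surgery was not discussed. Coders are blinded, and the second-round intraclass correlation for Expectations was 0.83.

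Much of this stands. A reader might infer that the manual is surgery-only, but its wider passages contradict that. A reader might also infer that the surgery-worded prompts always count. The documents do not support this either: the prompt on tubes and drains covers the time during surgery as well as after it, exact repeats go to OTHER, and the separate prompt on what happens without surgery fits the manual's OPTIONS example.

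The contradiction remains. The time-boundary reading is plausible but nowhere stated, and the sentence is worded as a requirement. The correlation shows that coders agreed with each other, not that they followed Table 2. Blinding does not settle scope. The restricted analysis comes after the intention-to-treat analysis and keeps patients who discussed both surgery and another treatment.

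**Conclusion.** The concern holds as a contradiction in the definition of a primary endpoint, which should be resolved before unblinding. A question about life after a single non-surgical treatment has no settled code and may score zero on EXPECTATIONS.

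A reader might go further and infer a bias in favour of the QPL. The documents do not show this. The inconsistency alone gives an odds ratio of 1.00 when the loss is equal in both arms, so a tilt needs shares that differ. It could also run against the QPL: the published protocol (Outcomes, Aim 2) notes that informed patients in some situations choose more conservative treatment, and an intervention arm that asks more about such treatment would lose more questions. The values from 1.04 to 1.66, and 0.85 in the reverse example, show only that unequal loss could be of the same order as the design odds ratio of 1.3. They rest on assumed shares and on 35% askers in both arms.

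**What to change.** Before unblinding:

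1. In the manual's EXPECTATIONS section, extend "it must relate to something after surgery" with the words *or another treatment under discussion*, to match Table 2. Align the LOGISTICS versus EXPECTATIONS boundary in Appendix A and in the LOGISTICS section.
2. Keep the existing rule that comparisons between options, including having against not having surgery, are OPTIONS.
3. Have the existing blinded coders re-read every question coded LOGISTICS or OTHER in all transcripts and recode those the rule captures. Do not select transcripts by treatment plan. The plan calls this a post-randomization variable and, for that reason, rejects stratifying a primary outcome by it. Selection would also miss patients planned for surgery who ask about additional treatment.
4. Report the EXPECTATIONS result with and without the recoding, and state beforehand which is primary. Table 2 is the pre-defined scheme, so the recoded count is the natural choice.

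The cost is a few sentences in the manual and a modest amount of extra blinded coding. The coding sheets already hold the text of each question, and counts for the other three primary question types do not change.

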Appendix A: Approaches vs. techniques

Use the following list of approaches vs. techniques to distinguish between OPTIONS and LOGISTICS AND TECHNICAL CONCERNS

Approaches: (Typically coded as OPTIONS)

- Open
- Minimally invasive
- Laparoscopic
- Endoscopic
- Robotic
- Endovascular or catheter based approach (includes TAVR/TAVI, EVAR or TEVAR)
- Single incision/single port
- Any option that involves interventional radiology instead of surgery

Techniques within a given approach: (Typically coded as LOGISTICS AND TECHNICAL CONCERNS)

- Staples versus stitches/hand sewn
- Type of stent or catheter
- Type of graft
- Reference to specific equipment/techniques – e.g. lasers, ablation, coagulation devices, ultrasound, ligasure, staplers, fluoro, dilators, scopes, cameras, specific needles or types of sutures

“OPTIONS” vs. “LOGISTICS AND TECHNICAL CONCERNS”

- OPTIONS includes approaches to surgery (“what”)
 - Look for things like: open, minimally invasive, laparoscopic, endoscopic, robotic, endovascular or catheter based approach (includes TAVR/TAVI, EVAR or TEVAR), single incision/single port, any option that involves interventional radiology instead of surgery
- LOGISTICS AND TECHNICAL CONCERNS includes techniques within an approach (“how”)
 - Look for things like: staples versus stitches/hand sewn, type of stent or catheter, type of graft, reference to specific equipment/techniques – e.g. lasers, ablation, coagulation devices, ultrasound, ligasure, staplers, fluoro, dilators, scopes, cameras, specific needles or types of sutures

“OPTIONS” vs. “RISKS/COMPLICATIONS” or “EXPECTATIONS”

- OPTIONS includes comparison of outcomes/expectations/risks
 - Look for words like better/worse than
 - Examples
 - “It’ll give a better chance?”
 - “So I would end up with paralysis if I didn’t have the surgery?”
- RISKS or EXPECTATIONS include questions about the risks of an option or what life will look like with a certain option, without comparison to the alternative
 - Example
 - “How likely is it that I will be paralyzed after surgery?”

“LOGISTICS AND TECHNICAL CONCERNS” vs. “EXPECTATIONS”

- LOGISTICS AND TECHNICAL CONCERNS includes questions about how things will work up to and through surgery
- EXPECTATIONS includes questions about the immediate post-operative stage onward

“RISKS/COMPLICATIONS” vs. “EXPECTATIONS”

- RISKS/COMPLICATIONS includes short-term, surgeon-defined effects from treatment
- EXPECTATIONS includes any questions that reference long-term effects/outcomes including recurrence and durability of procedure

“RISKS/COMPLICATIONS” vs. “LOGISTICS AND TECHNICAL CONCERNS”

- RISKS/COMPLICATIONS includes questions on bad outcomes
- LOGISTICS AND TECHNICAL CONCERNS includes how it’s going to get done – even if it’s serious or dangerous

PCORI – OPTION 5 Scoring Sheet

TRANSCRIPT ID	
RATER	

If a resident or another clinician is present *while* the enrolled study surgeon is in the room, incorporate the other clinicians' comments into your scoring. The goal is to code a conversation about a decision and this conversation includes many things.

Item 1. For the health issue being discussed, the clinician (1) draws attention to or re-affirms that alternate treatment or management options exist or that the (2) need for a decision exists. If the patient rather than the clinicians draws attention to the availability of options, the clinician responds by agreeing that the options need deliberation.

Score	Description	Notes
0	No alternatives mentioned, no mention of need for decision at all OR doesn't respond to patient question about alternatives (If they do any of the 3 things they get higher than 0 score) (MD states need to deliberate about alts. mentioned by patient to get higher than 0 score)	
1	Get credit for doing minimal effort of any: call attention to a decision, presents alternatives or responds to patient's question about alts.	
2	Must both say there is a decision AND there are options (more than one treatment is mentioned (can include palliative care or "do nothing")	
3	MD says we need to make a decision AND alternatives have been described as valid/not ridiculous (do nothing, or you die), does not make the point that this is preference sensitive	
4	MD says we need to make a decision AND that it's preference sensitive, AND alternatives have been well described as valid/not ridiculous (do nothing, or you die)	
		Item 1 Score =

Item 2. The clinician reassures the patient, or re-affirms, that the clinician will support the patient to become informed and to deliberate about the options. If the patient states that they have sought or obtained information prior to the encounter, the clinician supports such a deliberation process.

Score	Description	Notes
0	No mention of patient partnership, helping match preferences with treatment options	
1	MD conveys empathy or any acknowledgement of patient/family emotions/fears but does not make a point of how MD will provide support. Examples: "I know this is a difficult decision." "Many families of patients in the ICU tell me this can be an overwhelming experience."	
2	ANY: Mentions partnership, working together, matching surgeon expertise with patient values/goals	
3	MD provides clear indication of support, but not specific to decision-making. Example: "Our team cares about you and will do whatever we can to help you get through this."	
4	MD provides explicit support of patient/family in deliberation. Examples: "My role is to provide you with information and to guide you" "the decision that you and I make together"	
		Item 2 Score =

PCORI – OPTION 5 Scoring Sheet

TREATMENT OPTIONS	PROS	CONS
Option 1		
Option 2		
Option 3		

Add all treatment options discussed in table (including name of surgery) – even if the pros and cons are not discussed

Treatment plan at end of consult:	
--------------------------------------	--

Item 3. The clinician gives information, or checks understanding, about the pros and cons of the options that are considered reasonable (including taking ‘no action’), to support the patient in comparing the alternatives. If the patient requests clarification, explores options, or compares options, the clinician supports the process. (we are not going to worry about check for understanding here)

Score	Description	Notes
0	No pros and cons of any treatment described	
1	Pros OR cons of one option (no second option)	
2	Pros AND cons of one option (no second option) OR says two options but only gives the pros OR cons of one of the options	
3	Pros OR cons of both (all) options	
4	Pros AND cons of both (all) options. Must state ALL to get a 4.	
		Item 3 Score =

PCORI – OPTION 5 Scoring Sheet

Item 4. The clinician makes an effort to elicit the patient's preferences in response to the options that have been described. If the patient declares their preference(s), the clinician is receptive / supportive.

Score	Description	Notes
0	No phrases for deliberation, doesn't ask if patient has questions	
1	Asks if patient has "any questions" (cursory effort)	
2	Asks a more sophisticated question about whether the patient has questions/input "does this make sense to you?"	
3	Non-specific question for deliberation in unclear context	
4	Uses a clear question for deliberation – (how are you thinking about this, what is important to you now, how does this outcome seem to you?)	
		Item 4 Score =

Item 5. The clinician makes an effort to integrate the patient's preferences as decisions are made. If the patient indicates how best to integrate their preferences as decisions are made, the clinician is supportive. (this is about the recommendation/need to make a recommendation at some point, i.e. come back and reconsider, – do they make one and is it related to the patient's preferences, "this is what we are going to do AND this is why")

Score	Description	Notes
0	Makes a decision without patient input OR doesn't make a decision AND doesn't note that the decision will be deferred	
1	"It's up to you, you decide" OR gets deferred based on another test (clinical momentum)	
2	Decision gets deferred but recognition of patient preferences incorporated somehow	
3	Surgeon makes a plan, some suggestion that this would be aligned with pts values	
4	Surgeon makes a recommendation and says that it is concordant with what is important/valuable to the patient (uses what the patient has said to promote this as the right decision; says that this is the right decision based on a specific value the patient has)	
		Item 5 Score =

TOTAL OPTION SCORE						
Item	1	2	3	4	5	Total
Score						

Engaging Patients, Health Care Professionals, and Community Members to Improve Preoperative Decision Making for Older Adults Facing High-Risk Surgery

[name]; [name], BS; [name]; [name], BA; [name], MPH; [name], MPP

IMPORTANCE Older patients are at greater risk for postoperative complications, yet they are less likely than younger patients to ask questions about surgery.

◀ Invited Commentary
page 945

OBJECTIVE To design an intervention to improve preoperative decision making and manage postoperative expectations.

DESIGN, SETTING, AND PARTICIPANTS A Patient and Family Advisory Council (PFAC) was created to help identify preoperative decisional needs. The PFAC included 4 men and women who had previous experience with high-risk surgery as older patients or their family members; the PFAC met monthly at a local library from May 2014 to April 2015 to examine findings from a prior qualitative study and to integrate themes with PFAC members' experiences. Patient observations included 91 recorded conversations between patients and surgeons and 61 patient interviews before and after surgery. The PFAC members and other stakeholders evaluated 118 publicly available questions and selected 12 corresponding to identified needs to generate a question prompt list (QPL). Three focus groups, including 31 community members from diverse backgrounds, were conducted at community centers in Madison and Milwaukee, Wisconsin, to refine the QPL. A clinical pilot with 42 patients considering surgery was conducted in one outpatient surgical clinic in Madison.

MAIN OUTCOMES AND MEASURES Generation of a QPL to address patients' preoperative informational and decisional needs.

RESULTS Through exploration of qualitative data, the PFAC noted 3 critical problems. Patients and family members believed surgery had to be done, were surprised that postoperative recovery was difficult, and lacked knowledge about the perioperative use of advance directives. The PFAC identified a need for more information and decisional support during preoperative conversations that included clarification of treatment options, setting postoperative expectations, and advance care planning. The following 3 question prompt categories arose: "Should I have surgery?" "What should I expect if everything goes well?" and "What happens if things go wrong?" The final list included 11 questions within these domains, was understandable in English and Spanish, and was acceptable to patients in the clinic.

CONCLUSIONS AND RELEVANCE Through direct engagement of stakeholders, a QPL was created to address core decisional and informational needs of surgical patients. Future testing will evaluate whether this list can be used to improve patient engagement and reduce postoperative regret and conflict about postoperative treatments.

Author Affiliations: Department of Surgery, University of Wisconsin, Madison ([name], [name], [name], [name]); Denver Public Health, Denver Health and Hospital Authority, Denver, Colorado ([name]); Department of Family Medicine and Community Health, University of Wisconsin, Madison ([name]); Department of Pediatrics, University of Wisconsin, Madison ([name]); Department of Surgery, Oregon Health and Science University, Portland ([name]); Department of Medical History and Bioethics, University of Wisconsin, Madison ([name]).

Corresponding Author: [name], MPP, Department of Surgery, University of Wisconsin, [name] ([contact]).

JAMA Surg. 2016;151(10):938-945. doi:10.1001/jamasurg.2016.1308
Published online June 29, 2016.

Each year, approximately 500 000 Americans 65 years or older will have a high-risk operation, such as heart bypass or major cancer surgery.¹⁻³ Although many patients benefit from high-risk surgery, it carries a real potential for mortality and serious complications, particularly for older patients with multiple comorbidities. High-risk surgery can have other unintended consequences, including postoperative suffering, conflict about additional aggressive treatments, and receipt of unwanted interventions.^{4,5} Thus, much is at stake for patients in the decision to proceed.

Surgeons play an important role helping patients make preference-sensitive decisions. However, surgeons often miss opportunities for these discussions.⁶⁻¹¹ Patients report that “explanations are rushed, issues are not explained, [and] choices are not understood.”^{12(p6-6)} Although patients generally prefer involvement in the decision-making process, they frequently do not know how to engage.^{13,14} Patients who are activated receive more patient-focused care and are more likely to take part in collaborative decision making.^{15,16} This activation is especially critical for older patients, who are less likely to ask questions and less effective in ensuring that physicians attend to their concerns than younger patients.¹⁷

In other settings, question prompt lists (QPLs) can effectively improve patient engagement.¹⁸⁻²² Standardized lists of questions to ask the physician are available, but patients who have experience with surgery rarely participate in their development. To improve patient engagement in surgical decision making, we need to bridge the gap between patients’ need to make the consequences of surgery relevant to their lives and the surgeon’s goal of setting realistic expectations. Our objective was to design an intervention to improve preoperative decision making. By formalizing a partnership among patients, family members, and researchers, our Patient and Family Advisory Council (PFAC) developed a QPL to help older adults with high-stakes surgical decisions.

Methods

Development of a PFAC

Our PFAC served as consultants to provide feedback and reflection on our research, specifically to clarify concepts from previously generated qualitative data and to integrate the PFAC’s life experiences with identified priorities. We enlisted PFAC members through clinic nurses, surgeons, and hospital patient relations departments. We invited patients and family members of older patients who had experience with high-risk surgery and purposely selected a small group with strong literacy skills who could critically interpret abstracted data. Two members previously had major surgery (cardiac and neurologic) and 2 members were primary caregivers for patients who had surgery (vascular and oncologic). This group of 2 men and 2 women met monthly at a public library and received \$1000 for attendance at twelve 90-minute meetings (May 2014 to April 2015), independent review of materials, and travel.

Collection of qualitative data was approved by the institutional review boards of the University of Wisconsin and Partners Health Care System and the research ethics board of the

Key Points

Question Can researchers engage with surgical patients and family members to develop an intervention to address preoperative decisional and informational needs?

Findings The experiences of patients and family members were integrated through observational study and direct engagement to create a question prompt list for older adults considering high-risk surgery. Three decision-making needs were addressed, including clarification of treatment options, setting postoperative expectations, and advance care planning.

